### 5.3 STRATEGIES FOR RECRUITMENT AND RETENTION

Subjects will be recruited from several retirement communities and neurology practices. Recruitment materials will be used to find subjects. Participants will be compensated for their time at a rate of \$50 per completed study visit (up to two visits).

The target evaluable sample size for analysis is 400. We intend to enroll in such a manner that 200 are from the general community (and hence are most likely cognitively unimpaired) and 200 from Neurology clinics (and hence more likely to be cognitively impaired). 500 participants will be screened. The anticipated accrual rate is 50 participants per site per month. Enrollment will be completed in 6 months.

One to two US sites will be used in this study. Participants will be recruited from the general population and referred from neurology clinics. The study will be advertised in these areas using local fliers and print ads in regional papers. Participants will also be approached for participation if they are participating in other research at the sites that does not include the use of a drug or intervention to alter cognitive function and if the participant has not received cognitive testing (including MoCA, MMSE, Clock Drawing Test) within 6 months.

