#### Screening and Visit 1 (Day 1)

- Administrator #1 (consent, demographics + 14 min):
- Obtain informed consent of potential participant verified by signature on written informed consent form approved by the IRB. Eligible participants will be considered enrolled at the time of signing informed consent.
- Demographic information, medical history and current medication information collected.
- Screening tests and the DCTclock test will be administered in the following order:
  - Assessment of impairment of dominant hand- <1 min
  - Assessment of recreational drug and alcohol use- <1 min
  - Consent reading and comprehension assessment- 1 min
  - Hamilton-Veale Contrast Sensitivity test- 3 min
  - DCTclock test including demographics and recording of adverse device effects reported by participant or administrator- 3 min
  - Purdue Peg Board test- 5 min
- If a subject screen fails at any step, they will not complete the remaining assessments. Eligible subjects will then complete the study assessments.
- Administrator #2 (83 min for those who complete all assessments under version 1 of the protocol, 28 min for those who complete the bolded assessments below under version 2 of the protocol):
  - **MMSEworld- 10 min**
  - **MoCA- 8 min**
  - Benton Judgment of Line Orientation- 10 min
  - Rey Complex Figure- 15 min
  - D-KEFs Verbal Fluency Test- 10 min
  - **Digit Span and Reliable Digit Calculation - 5 min**
  - Block Designs- 10 min
  - **Trail Making Test A+B- 5 min**
  - Symbol Digit Modalities- 5 min
  - Geriatric Depression Scale (15 item version)- 5 min

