### 7.3.4 SCHEDULE OF EVENTS TABLE

Procedure	Screening/Visit 1	Visit 2	Administrator
Time	0	Within 1-4 weeks of visit 1	
Consent	X		1
Inclusion/Exclusion Criteria (Includes reading and comprehension assessments, dominant hand evaluation, and drug/alcohol use)	X	X	1
Hamilton-Veale Contrast Sensitivity	X	X	1
DCTclock Test and Demography	X	X	1
Assessment of adverse device effects	X	X	1
Purdue Peg Board	X	X	1
NP test battery:			

MMSEworld	X	X	2
MoCA	X	X	2
Benton Judgement of Line*	X	X	2
Rey Complex Figure*	X	X	2
D-KEFs Verbal Fluency*	X	X	2
Digit Span and Reliable Digit Calculation	X	X	2
Block Designs*	X	X	2
Trail Making Test	X	X	2
Symbol Digit Modalities*	X	X	2
Geriatric Depression Scale*	X	X	2

Assessments indicated with an asterisk (\*) above will only be given to participants who complete visit 1 under protocol version 1.

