## 10 STATISTICAL CONSIDERATIONS

The overall objective of this study is to demonstrate the safety and effectiveness of DCTclock as an adjunctive tool for use by clinicians to evaluate cognitive function in adults aged 55-95. From an effectiveness perspective, the study intends to prove that:

- a. DCTclock is non-inferior to the reference standard, MMSE, in identifying unimpaired and impaired test subjects.
- b. DCTclock shows test-retest reliability comparable to that of the MMSE.

The specific endpoints are as follows:

Primary endpoint: DCTclock and MMSE assessment of impaired, unimpaired or indeterminate/intermediate status. The primary analysis will assess agreement of DCTclock with the reference standard, MMSE, in identifying unimpaired and impaired test subjects.

Secondary endpoint: DCTclock scores, MMSE scores and assessment of DCTclock and MMSE impaired and unimpaired status at each of two time points. The secondary analysis will assess the DCTclock test-retest reliability and descriptively compare it to that of MMSE.

Additional endpoint: DCTclock scores, MMSE scores and neuropsychology battery scores. The goal of analysis on these endpoints is to assess construct validity of DCTclock. Specifically, the goal is to compare scores from the repeated administration of DCTclock to the repeated administration of a battery of neuropsychological tests, to characterize the psychometric properties of DCTclock and to compare those properties to the properties of MMSE.

Safety endpoint: incidence of device related adverse events.

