Negative Percent Agreement (NPA):  $(e+f+h+i)/(b+c+e+f+h+i)*100$  and its two-sided 95% Wilson confidence interval.

A quadratic weighted kappa score will be generated along with its Wald two-sided 95% confidence interval. This analysis will be repeated with the indeterminate/intermediate groups omitted.

Percent agreement for impaired:  $a/(a+d+g)*100$  and its two-sided 95% Wilson confidence interval.

Percent agreement for indeterminate/intermediate:  $e/(b+e+h)*100$  and its two-sided 95% Wilson confidence interval.

Percent agreement for unimpaired:  $i/(c+f+i)*100$  and its two-sided 95% Wilson confidence interval.

3. Within each of DCTclock and MMSE separately, participants will be categorized as impaired, not impaired or indeterminate/intermediate at each of the two measurements obtained on each participant. A 3-by-3 table, with the rows being the second reading status and with columns being the first reading cognitive status, will be generated as follows for each of DCTclock and MMSE:

		Reading 1			
Reading 2		Impaired	Indeterminate/ Intermediate	Unimpaired	Total
	Impaired	a	b	c	a+b+c
	Indeterminate/ Intermediate	d	e	f	d+e+f
	Unimpaired	g	h	i	g+h+i
	Total	a+d+g	b+e+h	c+f+i	a+b+c+d+ e+f+g+h+i

The Fisher-Freeman-Halton exact test will be used to assess if the cognitive classifications differ between reading 1 and 2 for each of DCTclock and MMSE. The null hypothesis is that reading 2 and reading 1 do not differ with respect to cognitive classifications.

4. If results show a significant difference between test and retest for DCTclock, that does not imply that DCTclock is less reliable than MMSE or other neuropsychological tests. The intraclass correlation for each of DCTclock test-retest difference, the MMSE test-retest difference, and neuropsychology battery variables' test-retest differences will be calculated. The test-retest weighted kappa statistic for determination of impaired status will also be calculated for DCTclock and MMSE. Results showing that DCTclock has similar or better ICC/ kappa than neuropsychological battery variables and MMSE will be considered as sufficient reliability of DCTclock.

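### The reliability success rule names an ICC that does not exist as written, leaves *similar* without a limit, and does not fix common participants for the six version 1-only tests

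*Protocol*

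**What the plan says.** Section 10 of the protocol lists, among the things the study intends to prove, that "DCTclock shows test-retest reliability comparable to that of the MMSE". The secondary endpoint paragraph of the same section then says that DCTclock reliability will be compared with that of MMSE descriptively. Section 10.4.1 likewise makes all DCTclock-MMSE comparisons after the primary one descriptive, with 95% confidence intervals where needed.

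Section 10.4.5 plans Deming regression, agreement percentages, weighted kappa and an exact test for each instrument separately. Item 4 then says that a significant test-retest difference for DCTclock would not show it to be less reliable than the other tests, and turns to two statistics:

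- "The intraclass correlation for each of DCTclock test-retest difference, the MMSE test-retest difference", and the same for the battery variables;
- "The test-retest weighted kappa statistic for determination of impaired status will also be calculated for DCTclock and MMSE".

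The verdict is: "Results showing that DCTclock has similar or better ICC/ kappa than neuropsychological battery variables and MMSE will be considered as sufficient reliability of DCTclock".

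On who takes what, the footnote to section 7.3.4 says that the asterisked tests "will only be given to participants who complete visit 1 under protocol version 1". These are Benton Judgement of Line, Rey Complex Figure, D-KEFs Verbal Fluency, Block Designs, Symbol Digit Modalities and the Geriatric Depression Scale. DCTclock, MMSE, MoCA, Digit Span and Trail Making are given to everyone.

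**The concern.** Item 4 is the only place where the protocol says what would count as adequate reliability, and it sets aside an adverse result from the earlier test-retest comparisons. The wording of that one sentence therefore carries the reliability claim. It has three weaknesses.

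1. The statistic is attached to the wrong quantity. An ICC separates between-person from within-person variance and needs at least two values per person. A test-retest difference gives one.
2. *Similar* has no margin, no interval on the difference and no minimum value. The rule also does not say whether every battery variable must be matched or only some.
3. Nothing limits each comparison to people who took both tests. For the six version 1-only tests, the comparator ICC comes from a subset, while DCTclock's may come from the whole sample.

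At stake is whether a statement that DCTclock is as reliable as its comparators follows from the data or from a choice of words after the data are in.

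**Working it through.** **The plan's own figures.** The protocol gives no ICC, margin, number of pairs or power for this rule, so there is none to reproduce. The sample size calculation in section 10.4.3 concerns the primary kappa only. One side check is possible, on which tests are restricted. The times in section 7.3.1 sum to 10+8+10+15+10+5+10+5+5+5 = 83 min for all ten tests. For MMSE, MoCA, Digit Span and Trails they sum to 10+8+5+5 = 28 min, which matches "28 min for those who complete the bolded assessments below under version 2 of the protocol". So six of ten tests, or six of nine without MMSE, are version 1-only.

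**Step 1: what *similar* decides.** Assumptions: true ICCs as shown, 400 people taking both tests, true-score correlation 0.6. The rule is read as passing when the DCTclock estimate is at least the comparator estimate minus d. Simulated pass probability (4,000 runs, one-way ICC):

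| True ICC, DCTclock vs comparator | d = 0 | d = 0.05 | d = 0.10 | d = 0.20 |
|---|---|---|---|---|
| 0.80 vs 0.80 | 0.51 | 0.98 | 1.00 | 1.00 |
| 0.75 vs 0.80 | 0.03 | 0.51 | 0.97 | 1.00 |
| 0.70 vs 0.80 | 0.00 | 0.04 | 0.50 | 1.00 |

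In the third row, the reading of one undefined word takes the result from near-certain failure to near-certain success. In the first row, the strictest reading fails an equally reliable test about half the time.

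**Step 2: what the study could resolve.** Approximate SE of an ICC = (1 − ICC²)/√n. For 0.70 and 0.80 the numerators are 0.51 and 0.36. Treating the estimates as independent, the 95% half-width for the difference is 1.96 × √(0.51² + 0.36²)/√n = 1.96 × 0.624/√n.

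- n = 400: 0.06
- n = 300: 0.07
- n = 200: 0.09
- n = 100: 0.12
- n = 50: 0.17

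The evaluable target is 400. Participants who miss visit 2 are not replaced (section 5.4.2), so 300 to 400 pairs is an assumed range for the tests given to everyone. The number of version 1 participants is not given; 50 to 200 is an assumed range.

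**Step 3: case mix in the version 1 subset.** Let r be the ratio of between-person SD in the subset to that in the full sample, with equal measurement error. A full-sample ICC of 0.80 becomes 0.80r²/(0.80r² + 0.20):

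- r = 0.7: 0.392/0.592 = 0.66
- r = 0.8: 0.512/0.712 = 0.72
- r = 0.9: 0.648/0.848 = 0.76
- r = 1.1: 0.968/1.168 = 0.83
- r = 1.2: 1.152/1.352 = 0.85

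The values of r are assumptions. Section 5.3 aims for an evaluable sample in which "200 are from the general community (and hence are most likely cognitively unimpaired) and 200 from Neurology clinics", but no such balance is stated for the participants seen under version 1, so r is not known to be 1.

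**The case against.** The strongest reply is that the comparison is secondary and labelled descriptive, that section 10.1 leaves detail to a statistical analysis plan not shown here, and that kappa, the agreement percentages and the Deming estimates all carry intervals. Part of this stands. The ICC form and bootstrap details would be ordinary content for that plan, and their absence alone would be no finding. But the protocol itself writes the sufficiency rule and says the study will prove comparability. The planned intervals are for each instrument separately, not for the difference on which the rule turns.

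A reader might infer four stronger things, and the documents support none of them.

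- *The rule can hardly fail.* It also requires DCTclock to match MMSE, and under strict readings (d = 0 to 0.05) a DCTclock at 0.70 against 0.80 passes with probability only 0.00 to 0.04.
- *Case mix favours DCTclock.* The bias can run either way. The size and composition of the version 1 group are not given, and nothing says it was narrower.
- *The battery ICCs come from different people.* Version 1 participants are a nested subset who also took DCTclock and MMSE at both visits, so matching is possible. The version 1 argument does not touch MMSE, MoCA, Digit Span or Trails.
- *The ICC cannot be obtained.* That is true of the literal text, but section 10.4.5 defines readings 1 and 2 and the intent is plain. It is a wording correction.

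**Conclusion.** The point holds in limited form. Section 10.4.5, item 4, ties a claim of sufficient reliability to a statistic specified on the wrong quantity and to a criterion without a limit. Section 10 calls the same comparison both something to prove and descriptive. The main consequence is that the conclusion depends on a later reading of *similar*: at assumed ICCs of 0.70 and 0.80 with 400 pairs, the pass probability covers the whole range from 0.00 to 1.00 as d goes from 0 to 0.20. For the six version 1-only tests, an unmatched comparison may also move by case mix, to between 0.66 and 0.85 for a test with full-sample ICC 0.80 at assumed SD ratios of 0.7 to 1.2, in a direction the documents do not determine. The ICC values, SD ratios, true-score correlation and numbers of pairs are all assumptions. The primary analysis is unaffected.

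**What to change.** In section 10.4.5, item 4:

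1. Replace the ICC of the test-retest difference with the ICC of reading 1 and reading 2, and name the form, for example two-way, absolute agreement, single measure. The form matters because item 4 itself allows for a systematic shift between visits, which absolute agreement penalises and consistency does not.
2. Compute each DCTclock-versus-comparator contrast on participants with both readings of both tests.
3. Report a paired bootstrap 95% confidence interval for each ICC difference, and for the kappa difference with MMSE, the only comparator for which kappa is planned.
4. For MMSE, either base the sufficiency conclusion on a limit for that interval fixed in advance, or drop the words of proof and sufficiency in sections 10 and 10.4.5 and report the comparison as descriptive. The limit is the sponsor's choice; with 300 to 400 pairs a half-width of about 0.06 to 0.07 is achievable at ICCs of 0.70 to 0.80.
5. Keep the version 1-only comparisons descriptive. The subset size is not given, and at 100 people the half-width would already be about 0.12.

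The cost is rewording and a bootstrap on data already planned for collection. If a limit is set, the reliability claim can fail by a stated criterion, and the version 1 comparisons use fewer people.

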#### 10.4.6 OTHER EFFECTIVENESS ANALYSIS

Psychometric Validation (construct validity). The goal of this analysis is to compare scores from the repeated administration of DCTclock to scores from the repeated administration of a battery of neuropsychological tests, to characterize the psychometric properties of DCTclock and to compare those properties to those properties of MMSE. Pearson correlation coefficients will be used for bivariate assessments of the relationship of DCTclock scores to neuropsychological test scores and for MMSE scores to neuropsychological test scores.

Scatter plots of DCTclock and MMSE scores vs. the scores of separate neuropsychological battery tests will be presented with a Deming regression line superimposed on the scatterplot.

#### 10.4.7 SAFETY ANALYSES

Safety analysis will be performed on the safety analysis set. Treatment emergent adverse events (TEAEs), which are events that started or worsened during or after the first DCTclock test, will be listed including start date of event and date of the DCTclock tests.

---

#### 10.4.8 BASELINE DESCRIPTIVE STATISTICS

Descriptive statistics of baseline characteristics will be presented for the ITT and Evaluable populations and descriptively compared between the two populations. Also, to be inspected will be the baseline characteristics for the ITT participants not in the Evaluable population.

---

#### 10.4.9 PLANNED INTERIM ANALYSES

There is no formal interim analysis for the study.

---

##### 10.4.9.1 EFFECTIVENESS REVIEW

There will be no review of effectiveness at the interim.

---

##### 10.4.9.2 SAFETY REVIEW

Testing with the study agent will be halted when three severe AEs determined to be “probably related” are reported to the sponsor. The study sponsor will notify investigators immediately when the third grade 3 event is reported and enrollment screens will stop accepting new study participants. The study sponsor will inform the FDA of the temporary halt and the disposition of the study. Given the low risk nature of the product, there will be no formal data safety monitoring board (DSMB) but there will be a safety Medical Monitor for the study.

---

#### 10.4.10 SUB-GROUP ANALYSIS

All above effectiveness analyses (with the exception of the formal hypothesis test of the weighted kappa) may be repeated by (1) age (below median age, at or above median age); (2) sex; (3) education level; (4) language fluency test score (below median, at or above median) (5) medical history; and (6) current medications.

In addition, it is expected that the DCTclock test’s ability to identify impaired participants exceeds that of MMSE when participants are mildly impaired. Thus, for participants who score unimpaired on MMSE but impaired on DCTclock, scores on the neuropsychology battery test may be further inspected as follows to assess how often the DCTclock yielded the correct diagnosis in these cases. Specifically, the following will be presented on this subset of participants (when available):

- Percentage of participants scoring in the impaired range on the MoCA test (25 or below)
- Percentage of participants scoring 1.5 standard deviations below the mean on two or more of the following tests (Benton Judgement of Line, Rey Complex Figure, DKEFs, Digit Span, Blocks, Trails, Symbol Digit).
- Percentage of participants 2 standard deviations below the mean on one of the following tests (Benton Judgement of Line, Rey Complex Figure, DKEFs, Digit Span, Blocks, Trails, Symbol Digit).

---

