### 10.4 DESCRIPTION OF STATISTICAL METHODS

#### 10.4.1 GENERAL APPROACH

All subjects will undergo testing with DCTclock, MMSE, and MoCA. A non-inferiority analysis using a two-sided tests (TOST) approach will be conducted comparing the quadratic weighted kappa between DCTclock and MoCA to the quadratic weighted kappa between MMSE and MoCA.

The remaining analysis comparing DCTclock to MMSE will be descriptive, providing two-sided 95% confidence intervals of important parameters when necessary.

Descriptive statistics include sample size, mean, standard deviation, median and quartiles for continuous variables, and counts and percents for categorical variables. All confidence intervals will be two-sided 95% confidence intervals, and all p-values will be two-sided, using a two-sided 0.05 level of significance. There will be no imputation of missing data. Statistical analysis will be conducted with R version 3.4 or higher.

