### 10.4.3 SAMPLE SIZE

Approximately 500 participants will be enrolled to obtain 400 evaluable participants. The evaluable sample size is the same as the evaluable sample size used in “De Novo Classification Request for Cognivue”. The primary null and alternative hypotheses are:

$$H_0: \kappa \leq 0.40 \quad \text{vs.} \quad H_1: \kappa > 0.40$$

where  $\kappa$  is the quadratic weighted kappa statistic calculated from the above DCT-MMSE classification table. Power for quadratic weighted kappa requires assumptions of the values on the diagonal and off-diagonal of the table, which is a large number of assumptions. Power will thus be calculated for the unweighted kappa which requires fewer assumptions. It is assumed that the quadratic weighted kappa will be similar to or larger in magnitude than the unweighted kappa and with similar standard error as the unweighted kappa, so the study will be powered to show that the unweighted kappa  $> 0.4$  with the expectation it will then be sufficiently powered to show that the quadratic weighted kappa  $> 0.4$ . An evaluable sample size of 400 subjects yields at least 80% power to reject the above null hypothesis at one-sided 0.025 level of significance under the assumptions that: (1) the true kappa is 0.52 or more; (2) the marginal percentage of participants categorized as impaired is between 20% and 42.5% for DCTclock; (3) the marginal percentage of participants categorized as impaired for MMSE is the same as that for DCTclock; (4) the marginal percentage of participants categorized as unimpaired for DCTclock is the same as the marginal percentage of participants categorized as impaired for DCTclock; (5) the marginal percentage of participants categorized as unimpaired for MMSE is the same as that for DCTclock; and (6) the marginal percentage of participants categorized as indeterminate is between 15% and 60% for each of DCTclock and MMSE and is equivalent between DCTclock and MMSE.

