### 10.4.4 SECONDARY AGREEMENT ANALYSIS

Agreement analysis: Additional agreement analyses between DCTclock and MMSE scores on detecting cognitive status will be carried out as follows:

- To better visualize the relationship between the two tests, the DCTclock and MMSE continuous scores will be plotted separately against the MoCA scores in a scatter plot, superimposed with a line of identity.
- Linear and rank linear regression analyses will be conducted and p-values with 95% CI will be calculated for the y-intercept and slope of each model. Either the Pearson (linear regression) or the Spearman (rank regression) correlation coefficients will be produced, and superimposed onto the scatter plots for each regression method, along with 95% confidence intervals and the estimated regression line.
- From Table I, the following statistics will be calculated for each of the tables (DCTclock vs MoCA and MMSE vs MoCA):

- Positive Percent Agreement (PPA) =  $a/(a+d+g)*100$  and its 95% Wilson CI
- Negative Percent Agreement (NPA) =  $(e+f+h+i)/(b+c+e+f+h+i)*100$  and its 95% Wilson CI.
- No formal hypotheses will be carried out on the PPA and NPA calculations, although 95% CIs will accompany them.

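### The battery check behind the expectation that DCTclock exceeds MMSE in mild impairment covers only one discordant cell; the reverse cell needs the same check

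*Protocol*

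**What the plan says.** Protocol section 10.4.10 expects that DCTclock's "ability to identify impaired participants exceeds that of MMSE when participants are mildly impaired". It draws the consequence that "for participants who score unimpaired on MMSE but impaired on DCTclock, scores on the neuropsychology battery test may be further inspected". The stated purpose is "to assess how often the DCTclock yielded the correct diagnosis in these cases".

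Three percentages follow for that subset:
- MoCA of 25 or below;
- 1.5 SD below the mean on two or more of seven named tests;
- 2 SD below the mean on one of those seven.

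No section plans the same figures for participants who are impaired on MMSE and unimpaired on DCTclock.

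Other sections do compare the two tests in both directions:
- Sections 10.4.1 and 10.4.2 compare the DCTclock-MoCA weighted kappa with the MMSE-MoCA weighted kappa.
- Section 10.4.4 gives positive and negative percent agreement with MoCA for each test.
- Section 10.4.6 plans Pearson correlations for the "relationship of DCTclock scores to neuropsychological test scores and for MMSE scores to neuropsychological test scores".

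**The concern.** The motivating sentence compares two tests, but the check looks only where DCTclock could have gained on MMSE. Within full disagreements between the tests, a participant whom the battery confirms as impaired is either a gain for DCTclock (MMSE missed the impairment) or a loss (DCTclock missed it). The plan counts the gains and has no row for the losses.

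A high confirmation rate in the one cell could then be read as support for the stated expectation, although the same rate can arise when DCTclock is no better than MMSE, or worse. What is at stake is the interpretation of a descriptive result; the primary analysis is not affected.

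**Working it through.** **The plan's own figure.** Section 10.4.10 gives no sample size or expected percentage. The only design figure nearby is in 10.4.3: at least 80% power for unweighted kappa 0.52 against 0.40, N = 400, one-sided 0.025. With the large-sample variance of kappa and power = Φ((0.12 - 1.96·SE0)/SE1), the least favourable symmetric tables give about 0.82 at 20% impaired and 0.81 at 42.5%. The figure reproduces, and the point does not rest on it.

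**What one cell can show.** Let F be the number DCTclock impaired/MMSE unimpaired, with f confirmed by a battery rule. Let R be the number MMSE impaired/DCTclock unimpaired, with r confirmed by the same rule. The plan reports f/F. The net for DCTclock among full disagreements is f - r, and r is never tabulated.

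**Illustration with counts (assumed, F = R = 20):**

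| Forward f/F | Reverse r/R | Net f - r |
|---|---|---|
| 12/20 (60%) | 6/20 (30%) | 12 - 6 = +6 |
| 12/20 (60%) | 12/20 (60%) | 12 - 12 = 0 |
| 12/20 (60%) | 16/20 (80%) | 12 - 16 = -4 |

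The Wilson 95% interval for 12/20 is 38.7% to 78.1% in every row. The reported result is identical and the conclusion differs.

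**Illustration with accuracies (all assumed).** Take 400 participants, half truly impaired, each test calling impaired or unimpaired only, errors independent given true status, and a battery rule with sensitivity 0.85 and specificity 0.80.

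- Equal tests (sensitivity 0.70, specificity 0.85). Forward cell: 200×0.70×0.30 = 42 impaired and 200×0.15×0.85 = 25.5 unimpaired. Confirmed: (42×0.85 + 25.5×0.20)/67.5 = 60%. The reverse cell is the same.
- DCTclock worse (0.60/0.75 against 0.75/0.90 for MMSE). Forward cell: 200×0.60×0.25 = 30 and 200×0.25×0.90 = 45; confirmed (25.5 + 9)/75 = 46%. Reverse cell: 200×0.40×0.75 = 60 and 200×0.75×0.10 = 15; confirmed (51 + 3)/75 = 72%.

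So 46% of the inspected cell is confirmed even when DCTclock is the worse test on both measures. The reverse cell shows this; the forward cell alone does not.

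**Size of the two cells.** Section 10.4.3 assumes that "the marginal percentage of participants categorized as impaired for MMSE is the same as that for DCTclock", with the unimpaired margins equal to the impaired ones, between 20% and 42.5%.

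- If disagreement is spread as by chance, each off-diagonal proportion is (1 - 0.52)·p_i·p_j. Each corner cell is then 400×0.48×0.20² = 7.7 or 400×0.48×0.425² = 34.7.
- Under a latent bivariate normal model solved for kappa 0.52, each corner cell is 0.07 or 14.9.

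Both models are symmetric, so the two corners are equal by construction. The stated margins do not require this. Move e participants around the table in a cycle: add e to impaired/unimpaired, unimpaired/indeterminate and indeterminate/impaired, and subtract e from their mirror cells. All margins, the diagonal and kappa stay unchanged.

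- At 20% margins, e can reach 7.68 (the corner itself), giving 15.4 against 0.
- At 42.5% margins, e can reach 400×0.48×0.425×0.15 = 12.24, giving 34.68 + 12.24 = 46.9 against 34.68 - 12.24 = 22.4.

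The imbalance can run in either direction.

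**Do other sections fill the gap?** For 10.4.4, "the following statistics will be calculated for each of the tables (DCTclock vs MoCA and MMSE vs MoCA"). The difference of the two positive agreements nets both directions, but only against MoCA. The correlations in 10.4.6 use the battery but do not classify the discordant participants by the seven-test rules.

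**The case against.** The strongest reply is that the analysis answers the question it poses: how often DCTclock was right in these cases. The comparative sentence is an expectation that gives a reason for looking. Section 10 lists what the study intends to prove (non-inferiority and comparable retest reliability), and superiority in mild impairment is not on that list. The check is optional, and DCTclock misses already count against it in the kappa comparison and in the positive agreement with MoCA. All of this stands, and it keeps the severity low. It does not remove the one-sidedness on the battery rules, where no section counts the losses.

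It is also true that the reverse cell does not isolate mild impairment. Neither cell is stratified by severity, and the two corners leave out disagreements that involve the indeterminate category. Reporting both cells makes the battery comparison two-sided; it does not turn it into a test of the expectation.

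Three stronger readings are tempting but unsupported:
- A reader might infer that the protocol claims superiority from this subset. It does not say so.
- A reader might infer from the equal margins in 10.4.3 that the unchecked cell is as large as the checked one. That needs an added symmetry assumption.
- A reader might object to the qualifier in "the following will be presented on this subset of participants (when available"), since five of the seven tests are given only to participants who complete visit 1 under protocol version 1. The qualifier already recognises incomplete batteries, and the denominator of an optional percentage is ordinary SAP detail. Any size put on it would need an assumed version split, correlation and mean shift.

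**Conclusion.** The point holds as a low-severity improvement. The planned percentage can show how often the battery confirms DCTclock when MMSE calls a participant unimpaired. It cannot support the view that DCTclock exceeds MMSE, because battery-confirmed impairment that MMSE found and DCTclock missed is not tabulated.

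That conclusion follows from the text of 10.4.10 and needs no model. The sizes shown (net +6, 0 or -4; 46% against 72%) are illustrations on assumed counts and accuracies, not predictions. The number of participants affected is uncertain: under the symmetric models each cell holds from under 1 to about 35, and the two cells need not be equal. No hypothesis, sample size or success criterion depends on this analysis.

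**What to change.** If this descriptive analysis is presented, report the same three percentages side by side for both discordant cells: DCTclock impaired/MMSE unimpaired, and MMSE impaired/DCTclock unimpaired. Give the denominator and the two-sided Wilson 95% interval for each. Add one sentence stating that the one-cell percentage is not evidence that DCTclock exceeds MMSE, and that neither cell is restricted to mild impairment. Keep the analysis descriptive.

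The cost is a few table rows and that sentence, from data already being collected; no new test, visit or sample size is needed. The downside for the sponsor is that the two-sided table may look less favourable to DCTclock. If the cells turn out very small, the intervals will be wide and the table will say little in either direction.
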